3. OBJECTIVES

3.1. Primary objectives

- To demonstrate the non-inferiority of the immune responses to three doses of *Pediarix*, *Hiberix* and *Prevenar 13* when co-administered with two doses of the PCV-free liquid HRV vaccine, as compared to when co-administered with the currently licensed lyophilized HRV vaccine, 1 month after Dose 3 of routine infant vaccines.

Criteria for non-inferiority:

- *Lower limits of the two-sided standardized asymptotic 95% confidence intervals (CIs) on the differences between groups (HRV Liq group minus HRV Lyo group) in the percentages of subjects with seroprotective concentrations (≥ 0.1 IU/mL) for each of anti-diphtheria (anti-D) and anti-tetanus (anti-T) antibodies are $\geq -10\%$ (clinical limit for non-inferiority),*
- *The lower limit of the two-sided standardized asymptotic 95% CI on the difference between groups (HRV Liq group minus HRV Lyo group) in the percentages of subjects with seroprotective concentration (≥ 10 mIU/mL) for antibodies against hepatitis B surface antigen (anti-HBs) is $\geq -10\%$ (clinical limit for non-inferiority),*
- *Lower limits of the two-sided standardized asymptotic 95% CIs on the differences between groups (HRV Liq group minus HRV Lyo group) in the percentages of subjects with seroprotective titers (≥ 8 ED₅₀) for each of anti-poliovirus serotypes 1, 2 and 3 antibodies are $\geq -5\%$ (clinical limit for non-inferiority),*

- Lower limits of the two-sided 95% CIs on the geometric mean antibody concentrations (GMC) ratios (HRV Liq group over HRV Lyo group) for antibodies against each of the pertussis toxoid (PT), filamentous hemagglutinin (FHA) and pertactin (PRN) antigens [anti-PT, anti-FHA and anti-PRN] are ≥ 0.67 (clinical limit for non-inferiority),
- Lower limits of the two-sided 95% CIs on the GMC ratios (HRV Liq group over HRV Lyo group) for each of the 13 *Streptococcus pneumoniae* (*S. pneumoniae*) serotypes are ≥ 0.5 (clinical limit for non-inferiority),
- The lower limit of the two-sided standardized asymptotic 95% CI on the difference between groups (HRV Liq group minus HRV Lyo group) in the percentages of subjects with concentration of antibodies against polyribosyl-ribitol-phosphate antigen (anti-PRP) $\geq 0.15 \mu\text{g/mL}$ is $\geq 5\%$,
- The lower limit of the two-sided standardized asymptotic 95% CI on the difference between groups (HRV Liq group minus HRV Lyo group) in the percentages of subjects with concentration of antibodies against anti-PRP $\geq 1.0 \mu\text{g/mL}$ is $\geq 10\%$ (clinical limit for non-inferiority).

- To rule out a 10% decrease in seroresponse to PT, FHA and PRN antigen when *Pediarix* is co-administered with PCV-free-liquid HRV vaccine compared to when *Pediarix* is co-administered with the currently licensed lyophilized HRV vaccine.
 - seroresponse is defined as the percentage of subjects showing an antibody concentration above a threshold that leads to 95% seroresponse in the control group (lyophilized HRV vaccine),
 - p-value on the difference in seroresponse between groups is $<2.5\%$ for each PT, FHA and PRN antigen (p-value is computed by integrating on the p-value for the null hypothesis that the seroresponse rate in the liquid group is $<85\%$ and the a-posteriori probability of the threshold in the lyophilized group).

3.2. Secondary objectives

Immunogenicity:

- To assess the immunogenicity of the PCV-free liquid HRV vaccine and currently licensed lyophilized HRV vaccine in terms of serum anti-rotavirus immunoglobulin A (IgA) antibody seropositivity rate at Visit 4, 3 months after Dose 2 of the HRV vaccine.
- To assess the immunogenicity of routine infant vaccines *Pediarix*, *Hiberix* and *Prevenar* 13 when co-administered with the PCV-free liquid HRV vaccine and currently licensed lyophilized HRV vaccine at Visit 4, 1 month after Dose 3 of routine infant vaccines.

Reactogenicity and safety:

- To assess the reactogenicity of the PCV-free liquid HRV vaccine and currently licensed lyophilized HRV vaccine in terms of general solicited adverse events (AEs) during the 8 day (Day 1-Day 8) follow-up period after each dose of HRV vaccine.
- To assess the safety of the study vaccines in terms of unsolicited AEs during the 31 day (Day 1-Day 31) follow-up period after each dose of HRV vaccine and serious adverse events (SAEs) during the entire study period.

4. ENDPOINTS**4.1. Primary endpoints**

- Immunogenicity with respect to components of the routine infant vaccines, one month after Dose 3 of routine infant vaccines (Visit 4):
 - Anti-D antibody concentration ≥ 0.1 IU/mL,
 - Anti-T antibody concentration ≥ 0.1 IU/mL,
 - Anti-HBs antibody concentrations ≥ 10 mIU/mL,
 - Anti-poliovirus types 1, 2 and 3 antibody titers ≥ 8 ED₅₀,
 - Anti-PT, anti-FHA and anti-PRN antibody concentrations expressed as GMCs,
 - Anti-pneumococcal serotypes (1, 3, 4, 5, 6A, 6B, 7F, 9V, 14, 18C, 19A, 19F, 23F) antibody concentrations expressed as GMCs,
 - Anti-PRP antibody concentrations ≥ 0.15 μ g/mL,
 - Anti-PRP antibody concentrations ≥ 1.0 μ g/mL.
- Difference in seroresponse with respect to PT, FHA and PRN antigen components one month after Dose 3 of routine infant vaccines (Visit 4):
 - Seroresponse to anti-PT, anti-FHA and anti-PRN.

4.2. Secondary endpoints

- Serum anti-rotavirus IgA antibody seropositivity 3 months after Dose 2 of HRV vaccine (Visit 4).
 - Serum anti-RV IgA antibody concentrations ≥ 20 U/mL and ≥ 90 U/mL 1-2 months after Dose 2.
- Immunogenicity with respect to components of the routine infant vaccines, one month after Dose 3 of routine infant vaccines (Visit 4).
 - PT, anti-FHA and anti-PRN antibody concentrations ≥ 2.693 IU/mL, ≥ 2.046 IU/mL and ≥ 2.187 IU/mL, respectively.
 - Anti-pneumococcal serotypes (1, 3, 4, 5, 6A, 6B, 7F, 9V, 14, 18C, 19A, 19F, 23F) antibody concentrations ≥ 0.35 μ g/mL for the ELISA,

- Anti-D, anti-T, anti-PRP and anti-HBs antibody concentrations expressed as GMCs and anti-poliovirus types 1, 2 and 3 antibody concentrations expressed as Geometric Mean Titers (GMTs).
- Occurrence of general solicited AEs during the 8 day (Day 1-Day 8) follow-up period after each dose of HRV vaccine.
- Occurrence of unsolicited AEs within 31 days (Day 1-Day 31) after any dose of HRV vaccine, according to the Medical Dictionary for Regulatory Activities (MedDRA) classification.
- Occurrence of SAEs from Dose 1 of study vaccines up to study end.

5. ANALYSIS SETS

All analyses will be performed per treatment actually administered at Dose 1.

5.1. Definition

5.1.1. Exposed Set

The Exposed Set (ES) will include all subjects with at least one study vaccine administration documented. A safety analysis based on the ES will include all vaccinated subjects.

An immunogenicity analysis based on the ES will include all vaccinated subjects for whom immunogenicity data is available.

5.1.2. Per-protocol Set for analysis of immunogenicity (PPS)

The PPS for immunogenicity will include all eligible subjects from the ES:

- who have received the study vaccines according to their random assignment,
- who comply with the vaccination schedule of routine infant vaccines and HRV vaccines as per [Table 5](#),
- for whom the routine infant vaccines were administered according to the protocol as per [Table 4](#),
- for whom the HRV vaccine liquid or lyophilized formulation was administered according to protocol,
- who have not received a vaccine not specified or forbidden in the protocol up to Visit 4 blood sampling,
- who had not received medication forbidden by the protocol up to Visit 4 blood sampling,
- whose underlying medical condition(s) was (were) not forbidden by the protocol up to Visit 4 blood sample,

- for whom data concerning immunogenicity endpoint measures are available. This will include subjects for whom assay results are available for antibodies against at least one routine infant vaccine antigen component,
- who comply with the blood sampling schedule after the 3rd dose of Pediarix, Hiberix and Prevenar 13 as per [Table 5](#),
- who have no concomitant infection up to Visit 4 blood sample, which may influence the immune system.

Table 4 Dosage and administration

Type of contact and time-point	Study group	Treatment name	Volume to be administered	Route ¹	Site		
					Location	Directionality ²	Laterality
Visit 1, Visit 2	HRV Liq	HRV Liquid	1.5 ml	O	Not applicable	Not applicable	Not applicable
Visit 1, Visit 2	HRV Lyo	HRV Lyophilized	1 ml	O	Not applicable	Not applicable	Not applicable
Visit 1, Visit 2, Visit 3	HRV Liq, HRV Lyo	Pediarix	0.5 ml	IM	Thigh	Upper	Right
Visit 1, Visit 2, Visit 3	HRV Liq, HRV Lyo	Hiberix	0.5 ml	IM	Thigh	Anterolateral	Right
Visit 1, Visit 2, Visit 3	HRV Liq, HRV Lyo	Prevenar 13	0.5 ml	IM	Thigh	Lower	Left

¹Oral (O), Intramuscular (IM)² Directionality is a qualifier for further detailing the location of the vaccine administration.**Table 5 Maximum allowed interval between visits**

Interval	Allowed length of interval
Visit 1→Visit 2	49 days-83 days after Dose 1 of study vaccines 1
Visit 2→Visit 3	56 days-83 days after Dose 2 of study vaccines 1
Visit 3→Visit 4	21 days-48 days after Dose 3 of study vaccines 1
Visit 3→ESFU	180 days-210 days after Dose 3 of study vaccines

¹ Subjects will not be eligible for inclusion in the Per-Protocol Set (PPS) for analysis of immunogenicity, if they make the study visit outside this interval. This is not applicable for the interval between Visit 3 and ESFU.

5.2. Criteria for eliminating data from Analysis Sets

Elimination codes are used to identify subjects to be eliminated from analysis. Detail is provided below for each sets.

5.2.1. Elimination from Exposed Set (ES)

Code 1030 (Study vaccine not administered at all) and code 900 (invalid informed consent or fraud data) will be used for identifying subjects eliminated from ES.

2040	
Administration of any medication forbidden by the protocol:=>
 
 • Any investigational or non-registered product (drug or vaccine) other than the study vaccines used during the study period between the first vaccination at Visit 1 to the blood sampling at Visit 4. • Immunosuppressants or other immune-modifying drugs administered chronically (i.e., more than 14 days) during the study period between Visit 1 to Visit 4. For corticosteroids, this will mean prednisone ≥ 0.5 mg/kg/day, or equivalent. Inhaled and topical steroids are allowed. • Immunoglobulins and/or any blood products administered during the study period between the first vaccination at Visit 1 to the blood sampling at Visit 4. • Administration of long-acting immune-modifying drugs between the first vaccination at Visit 1 to the blood sampling at Visit 4 (e.g., infliximab).
2070	Concomitant infection not related to the vaccine which may influence immune response => who have concomitant infection up to Visit 4 blood sample, which may influence the immune system (GE episodes not to be considered).
2080	Non-compliance with vaccination schedule => Subjects that did not comply with the vaccination interval as stated in Table 5 (including wrong and unknown dates):
2090	Non-compliance with the blood sampling schedule (including wrong and unknown dates) => Blood sample not collected within 21 days-48 days after the third dose of the co-administered vaccines (Visit 4).
2100	Essential serological data missing => No serological results at all available post-vaccination
2120	Obvious incoherence or abnormality or error in data =>BS result available while BS not taken

5.2.2.2. Right censored Data

Not applicable

5.2.2.3. Visit-specific censored Data

Not applicable

5.3. Important protocol deviation not leading to elimination from per-protocol analysis set

Important protocol deviations not leading to elimination from PPS for immunogenicity will be reported by groups. This includes but is not limited to

- Forced randomization: In case of supplies shortage for the next assigned vaccine according to the randomization schedule at the clinical site, the randomization system will use the forced randomization procedure in order to continue to enrol and vaccinate subjects. The system moves seamlessly to the next treatment/randomization number for which vaccine supplies are available. The site will not be aware of the forced randomization event.
- Manual randomization: In case the randomization system is unavailable, the investigator has the option to perform randomization by selecting supplies available at the site according to a pre-defined rule.
- Short follow-up: subjects who completed the last study contact before the minimum length of follow-up requirement (180 days).
- HRV vaccination without documentation of solicited symptoms i.e. for a HRV vaccine dose administered, at least one solicited symptom is not documented as being present or absent.

The full list of reportable protocol deviations is available in the study protocol deviation management plan.

6. STATISTICAL ANALYSES

Note that standard data derivation rule and stat methods are described in annex 1 and will not be repeated below.

6.1. Demography

6.1.1. Analysis of demographics/baseline characteristics planned in the protocol

The median, mean, range and standard deviation of age (in weeks) at each study vaccine dose and of the gestational age will be computed by group. The median, mean and standard deviation of length (in centimeters) and weight (in kilograms) at Visit 1 will be computed by group. The racial and sex composition of the subjects will be presented.

The distribution of subjects enrolled among the study centers will be tabulated as a whole and per group.

The number of subjects who withdraw from the study will be tabulated by group according to the reason for drop-out.

The deviations from specifications for age and intervals between study visits will be tabulated by group.

6.1.2. Additional considerations

All demography summaries will be generated for the ES. The summary of age, height, weight, race and sex will also be provided for the PPS. Number and reason for elimination from PPS will be tabulated by group. Summary of important protocol deviations not leading to elimination will be provided by groups for the PPS.

6.2. Exposure

6.2.1. Analysis of exposure planned in the protocol

Not applicable

6.2.2. Additional considerations

The number of doses administered will be tabulated for each group.

6.3. Immunogenicity

6.3.1. Analysis of immunogenicity planned in the protocol

The primary analysis will be based on the PPS for analysis of immunogenicity. An analysis on the ES will be performed only if, in any group, more than 5% of the vaccinated subjects with immunological data are excluded from the PPS for immunogenicity.

6.3.1.1. Within group analysis

For each treatment group, one month after Dose 3 of routine infant vaccines at Visit 4 (Month 5) time-point:

- Seroprotection rates against HBsAg, diphtheria toxoid, tetanus toxoid, PRP antigen and poliovirus types 1, 2 and 3 (with exact 95% CI) will be calculated.
- Seropositivity rates and their exact 95% CIs for antibodies against PT, FHA, PRN, anti-rotavirus, S. pneumoniae serotypes 1, 3, 4, 5, 6A, 6B, 7F, 9V, 14, 18C, 19A, 19F, 23F and HBsAg will be tabulated.
- Percentage of subjects with anti-pneumococcal serotypes (1, 3, 4, 5, 6A, 6B, 7F, 9V, 14, 18C, 19A, 19F, 23F) antibody concentrations $\geq 0.35 \mu\text{g/mL}$ with 95% CI will be calculated.
- Percentage of subjects with anti-PRP antibody concentrations $\geq 1.0 \mu\text{g/mL}$ will be calculated with 95% CI.

- Percentage of subjects with anti RV IgA antibody concentration ≥ 90 U/mL will be calculated with 95% CI.
- GMC/GMT with 95% CI will be tabulated for antibodies against each antigen.

The above mentioned descriptive analyses will also be performed by race and sex.

The distribution of antibody concentrations/titers for each appropriate serotype/antigen will be displayed using tables and/or reverse cumulative distribution curves.

For anti-HBs antibodies, an analysis will be done according to vaccination history to Hepatitis B vaccine.

6.3.1.2. Between group assessment

For each treatment group, one month after Dose 3 of routine infant vaccines at Visit 4 (Month 5) time-point:

- Two-sided asymptotic standardized 95% CIs for the difference in the percentage of subjects with titer/concentration above or equal to pre-specified clinical thresholds will be computed (HRV Liq group minus HRV Lyo group).
- The two-sided 95% CIs for the group GMC/GMT ratio (HRV Liq group over HRV Lyo group) will be computed using an ANOVA model on the logarithm10 transformation of the concentrations. The ANOVA model will include the vaccine group as fixed effects. In addition, for anti-HBs, the model will include the Hepatitis B vaccination history as co-variable.
- For the group comparison in anti-PT, FHA, PRN seroresponse at one month post dose 3, P-value for testing $H_0: P \leq 85\%$ vs. $H_1: P > 85\%$ ($P = \%$ of subjects in HRV liq group with seroresponse (above a threshold that leads to 95% seroresponse in the HRV lyo group) will be computed. P-value will be computed by integrating on the p-value for the null hypothesis that the seroresponse rate in the HRV lyo group is $< 85\%$ and the a-posteriori probability of the threshold in the HRV liq group.

6.3.1.3. Statistical methods

- The exact 95% CIs for a proportion within a group will be based on the method by Clopper [see section 11.1].
- The standardized asymptotic CI for the group difference in proportion is the method 6 described in the Newcombe paper [see section 11.1]
- The 95% CIs of the group GMC/GMT ratios will be computed using an ANOVA model on the logarithm10 transformation of the concentrations/titers. The ANOVA model will include the vaccine group as fixed effects. In addition, for anti-HBs, the model will include the Hepatitis B vaccination history as co-variable.
- The 95% CI for GMTs/GMCs will be obtained within each group separately. The 95% CI for the mean of log-transformed titer/concentration will be first obtained assuming that log-transformed values were normally distributed with unknown

variance. The 95% CI for the GMTs/GMCs will then be obtained by exponential-transformation of the 95% CI for the mean of log-transformed titer/concentration.

- P-value for seroresponse endpoint will be computed by integrating on the p-value for the null hypothesis that the seroresponse rate in the HRV lyo group is <85% and the a-posteriori probability of the threshold in the HRV liq group.

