5.2.2.2.1. Study group and treatment number allocation

The target will be to enrol 1280 eligible subjects who will be randomly assigned to two study groups in a (1:1) ratio (approximately 640 subjects in each group).

Allocation of the subject to a study group at the investigator site will be performed using SBIR. The randomization algorithm will use a minimization procedure accounting for the center and the study as minimization factors. Minimization factors will have equal weight in the minimization algorithm.

After obtaining the signed and dated ICF from the subject's parent/LAR and having checked the eligibility of the subject, the site staff in charge of the vaccine administration will access SBIR. Upon providing the subject identification number, the randomization system will determine the study group and will provide the treatment number to be used for the first dose.

The number of each administered treatment must be recorded in the eCRF on the Vaccine Administration screen.

When SBIR is not available, please refer to the SBIR user guide or the Study Procedures Manual (SPM) for specific instructions.

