10.3. Determination of sample size

The target sample size is 832 subjects evaluable for immunogenicity analyses at Visit 4 (416 subjects in each group). Assuming that approximately 35% of enrolled subjects might withdraw or not be evaluable for analyses of immunogenicity, the target sample size to be enrolled is 1280 subjects (640 subjects in each group).

The primary objective of this study is to demonstrate the immune response elicited to all antigens contained in each of the routine infant vaccines *Pediarix*, *Hiberix* and *Prevenar 13* when co-administered with PCV-free liquid HRV vaccine is non-inferior to that elicited when co-administered with the lyophilized HRV vaccine.

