6.3.2. Additional considerations

Summaries will be generated by frequent race and by gender using PPS. Note that a race category is considered if it includes more than 40 subjects. Infrequent race categories will be combined together and summarized if it includes more than 40 subjects.

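### Allocation is minimized by center, but the ANOVA behind the 16 co-primary GMC ratios omits center, so its valid intervals are slightly too wide if antibody levels differ between centers

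*SAP*

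**What the plan says.** **Allocation.** Under Protocol 5.2.2.2.1, subjects are "randomly assigned to two study groups in a (1:1) ratio", and "The randomization algorithm will use a minimization procedure accounting for the center and the study as minimization factors". Study is constant within this trial, so center is the only factor that varies.

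**Model for GMC/GMT ratios.** SAP 6.3.1.3 specifies an ANOVA on log10 values: "The ANOVA model will include the vaccine group as fixed effects". One covariate is allowed, for one antigen: "In addition, for anti-HBs, the model will include the Hepatitis B vaccination history as co-variable". The anti-HBs GMC is a secondary endpoint. The same model appears in SAP 6.3.1.2 and in Protocol 10.7.2 and 10.9.1, so the documents agree with each other.

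**Use of center in the analysis.** SAP 6.1.1 plans only a description: "The distribution of subjects enrolled among the study centers will be tabulated as a whole and per group".

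**Analysis set.** SAP 6.3.1 states: "The primary analysis will be based on the PPS for analysis of immunogenicity". Protocol 10.3 sizes the trial "Assuming that approximately 35% of enrolled subjects might withdraw or not be evaluable for analyses of immunogenicity", which takes 640 enrolled per group to 416 evaluable.

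**The concern.** When a factor is balanced by design and then left out of the model, the treatment difference is estimated more precisely than its standard error shows. The between-center variation cancels from the difference but stays in the residual variance. Intervals are then too wide and coverage exceeds 95%.

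At stake is the reported precision of the 16 co-primary GMC ratios and the secondary GMC/GMT ratios, and the match between how the trial allocates and how it analyzes. There is no inflated false-positive risk. A center term is also easier to defend if it is fixed in advance than if it is added once results are known.

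**Working it through.** **Inputs.** From Protocol Table 18: 416 evaluable per group; PRN margin 0.67 with log10 SD 0.409 (the GMC row with least power); seven serotypes with margin 0.5 and SD 0.549. The true ratio is 1 and the one-sided error 2.5%. The share of log-titer variance due to center (R²) and the number of centers are not given, so I used R² of 0 to 10% and 20 to 64 centers.

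**Step 1: reproduce Table 18 for PRN.**
- SE = 0.409 × √(2/416) = 0.0284.
- Distance to the margin = −log10(0.67) = 0.1739, which is 6.13 standard errors.
- Noncentral t with 830 df gives a type II error of 0.0016%.
- For SD 0.549 and margin 0.5 it is below 0.000001%.

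Every GMC row agrees with the stated 0.0%.

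**Step 2: exact balance within center.** The model estimates the variance of the difference as 2σ²/n. The actual variance is 2σ²(1 − R²)/n. The planned interval is therefore too wide by 1/√(1 − R²) − 1:

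| R² | Planned CI too wide by | Coverage of planned CI | One-sided error |
|---|---|---|---|
| 2% | 1.0% | 95.2% | 2.39% |
| 5% | 2.6% | 95.6% | 2.22% |
| 10% | 5.4% | 96.1% | 1.94% |

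These are upper bounds on the gain, because the per-protocol set follows a planned 35% loss that disturbs the balance.

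**Step 3: simulation with that loss.** Each cell has 5000 runs, 1280 enrolled, allocation balanced within center and 35% random loss. The entries are the center-adjusted CI width divided by the planned width. Unequal centers have Dirichlet(1) sizes, and those with fewer than 10 evaluable subjects are pooled. Equal centers are not pooled.

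| R² | 20 unequal | 60 unequal | 20 equal | 64 equal |
|---|---|---|---|---|
| 0% | 1.0035 | 1.0068 | 1.0041 | 1.0143 |
| 2% | 0.9946 | 0.9985 | not run | not run |
| 5% | 0.9809 | 0.9856 | 0.9798 | 0.9888 |
| 10% | 0.9585 | 0.9641 | 0.9553 | 0.9629 |

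With equal centers, the group-only interval covered 95.3–95.5% at R² = 5% and 95.8–96.0% at 10%. The adjusted interval stayed near 95%. With unequal centers, the 0.67 margin was met in every run under both models.

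**Step 4: break-even.** Linear interpolation between R² = 0 and 2% (unequal centers):
- 20 centers: 0.0035/(1.0035 − 0.9946) × 2% ≈ 0.8%.
- 60 centers: 0.0068/(1.0068 − 0.9985) × 2% ≈ 1.6%.

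Below these shares, adjusting slightly widens the interval.

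**Step 5: effect on the decision.** The PRN lower limit at a true ratio of 1 is 10^(−1.963 × 0.0284) = 0.880 as planned. At R² = 10% it is at most 10^(−0.0557 × √0.90) = 0.886, against 0.67. Type II error falls from 0.0016% to 0.0003%, so Table 18 still reads 0.0%.

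**The case against.** The strongest reply is that nothing is broken. The model is valid, is stated consistently in four places, and matches the two-group normal test used for power. The GMC criteria already have essentially 100% power. Of the 9.6% total type II error in Table 18, 4.8% + 4.4% = 9.2% belongs to the two anti-PRP proportions, which this ANOVA does not touch. All of that stands and is why the point is minor.

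Four further arguments deserve an answer:

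- **The gain is not assured.** This stands: it depends on a center variance that the documents do not give, and below roughly 1–2% the adjustment loses a little precision.
- **The match to allocation is partial.** This also stands. The 8 proportion criteria and 3 seroresponse tests, 11 of 27 co-primary criteria, remain unadjusted. With many small centers the pooled category can absorb about half of them.
- **Balance is weaker than assumed.** SAP 5.3 keeps subjects with forced or manual randomization in the per-protocol set. This shrinks the gain within the upper bounds of Step 2 but does not reverse the argument.
- **A protocol amendment is out of proportion.** This has less force. Protocol 10.10 provides for changes to the statistical plan to be described and justified in the study report, and SAP section 9 already records one.

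**Conclusion.** The point holds as an optional precision improvement. Center drives allocation and is absent from the model, without explanation. If center explains 5% of log-titer variance, adjustment would narrow the GMC intervals by about 1–2% after the planned loss. At 10% it would narrow them by about 4%. If centers do not differ, it would widen them by 0.4–0.7% with unequal centers and pooling, and by up to 1.4% in the case of 64 equal centers.

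These figures rest on assumed center variances, numbers and sizes, on loss unrelated to group or response, and on near-balance within center. No sample size or power figure changes and, at the planning assumptions, neither does any non-inferiority conclusion.

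**What to change.** In SAP 6.3.1.2 and 6.3.1.3, and in Protocol 10.7.2 and 10.9.1 if the protocol is amended, specify:

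> ANOVA on log10 concentration/titer with vaccine group and center as fixed effects, plus hepatitis B vaccination history for anti-HBs. Centers with fewer than 10 evaluable per-protocol subjects (both groups combined) are pooled into one category. This rule is fixed before group-level immunogenicity data are seen.

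Keep the group-only ANOVA as a sensitivity analysis. If the change is made in the SAP alone, record it in SAP section 9. If the sponsor prefers the present model, one sentence giving the reason would close the point.

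The threshold of 10 is a judgment; the documents set none for centers. The SAP's cutoff for race ("Note that a race category is considered if it includes more than 40 subjects") would be a poor substitute. At R² = 5%, pooling centers below 40 cuts the narrowing from 1.9% to 1.6% with 20 centers and from 1.4% to 0.5% with 60.

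The cost is one model term, one pooling rule, a second run of each GMC/GMT ratio, and one residual degree of freedom per additional center category. In the simulation with unequal centers and pooling, about 814 (20 centers) or 800 (60 centers) of roughly 830 remain. No change is asked for the proportion criteria or the seroresponse tests.
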